8 STATISTICAL CONSIDERATIONS

8.1 STATISTICAL HYPOTHESES

Specific Aim 1: Among youth 6-17 years with an elevated BP measurement ($\geq 95^{\text{th}}$ percentile or $\geq 130/80$ mmHg), to evaluate the effectiveness of the adapted PedsBP for repeat BP measurement:

Hypothesis 1: Youth with elevated BP measured at a PedsBP intervention clinic will be more likely to have a repeat BP

measurement during their visit as compared to those attending usual care clinics.

Hypothesis 2: Youth with elevated BP measured at a high-intensity PedsBP clinic will be more likely to have a repeat BP measurement during their visit, as compared to those attending low-intensity PedsBP clinics.

Specific Aim 2. Among youth 6-17 years meeting criteria for HTN, to evaluate the effectiveness of the adapted PedsBP for improving HTN recognition:

Hypothesis 3: Youth meeting criteria for HTN at a PedsBP intervention clinic will be more likely to be clinically recognized within 6 months of their index visit, as compared to those attending usual care clinics.

Hypothesis 4: Youth meeting criteria for HTN at a high-intensity PedsBP clinic will be more likely to be clinically recognized within 6 months of their index visit, as compared to those attending low-intensity PedsBP clinics.

Table 2. Study Contrasts and Outcomes by Hypothesis

Hypothesis	Contrast	Denominator	Outcome(s)	Data source(s)
H1	CDS (low- or high-intensity) versus Usual care	First BP at visit $\geq 95^{\text{th}}$ percentile (ages 6-12) or $\geq 130/80$ mmHg (ages 13-17)	Repeat BP measured and recorded at same visit	Automated BP data from EHR or CDS
H2	CDS low-intensity versus CDS high-intensity			
H3	CDS (low- or high-intensity) versus Usual care	BP at visit and at least 2 of 4 prior BPs, within last 2 years, $\geq 95^{\text{th}}$ (ages 6-12) or $\geq 130/80$ mmHg (ages 13-17)	HTN recognition within 6 months of meeting criteria for HTN	Automated data from EHR or CDS
H4	CDS low-intensity versus CDS high-intensity			
Secondary / Exploratory	CDS (low or high intensity) versus Usual care	BP at visit and at least 2 of 4 prior BPs, within last 2 years, $\geq 95^{\text{th}}$ (ages 6-12) or $\geq 130/80$ mmHg (ages 13-17)	Management within 6 months of meeting criteria for HTN including: Lifestyle counseling, Referrals, Medications for HTN, Diagnostic imaging / BP at 12 months Provider satisfaction	Automated data from EHR or CDS, limited chart review and provider survey

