8.3 POPULATIONS FOR ANALYSES

We will continue to engage with EH leadership to ensure the active participation of EH clinics. EH leadership support for this project, as evidenced in the letters of support, ensures the participation of primary care clinics.

Patients 6 to 17 years of age with a BP recorded at a participating EH primary care clinic will be eligible and automatically enrolled on the basis of data recorded in the EHR and captured by the PedsBP CDS. Given that one of the primary purposes of the study is to test the effectiveness of the different intervention approaches, including a high-intensity intervention with additional outreach and engagement of clinicians and rooming staff, we do not plan to conduct additional recruitment or retention activities.

Aim 1 outcomes will be assessed in the context of care provided at the index visit with an isolated hypertensive BP recorded. Aim 2 outcomes will be assessed over a period of 6 months following when a patient meets criteria for HTN. Clinical recognition of HTN, dietitian or other lifestyle referral and lifestyle counseling will be assessed based on care received. There will be no additional efforts to recall patients for additional study visits. For subjects with no follow-up visits, Aim 2 outcomes will be assessed based on clinical actions at the index visit.

Providers and rooming staff will be invited to participate in surveys and in-depth interviews through email or in-person recruitment by EH study staff. Surveys and interviews will be conducted at the time of recruitment as well as through a follow-up survey at the end of the intervention period. We will work with clinic administrative staff as necessary to help coordinate interviews and surveys with clinicians and rooming staff in a way that is not disruptive to regular clinic operations.

Data sources

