The dependent variable for Aim 1 (BP_Remeasure) is a binary indicator of post-implementation re-measurement of BP at the index visit at which the elevated BP occurred. For H1 this endpoint will be predicted by a fixed effect study arm term (TeenBP_j) contrasting low- plus high-intensity PedsBP clinics with usual care clinics, stratification factors used in the clinic randomization (StratFactors_j), and patient-level covariates of age, sex, and SBP percentile of the elevated BP. A random intercept for clinics is included (u_{j0}) to account for the clinic-level randomization. The analysis for H2 will contrast high- and low-intensity clinics (HighVsLow_j) and exclude usual care clinics from the analysis, but otherwise be similar to H1. Statistically significant study arm contrasts (alpha=.05) and parameters in the expected direction will support the H1 and H2 predictions stated for Aim 1.

Hypotheses 3 and 4 for **Aim 2** posit that patients who newly meet HTN criteria at clinics with low- or high-intensity PedsBP CDS will be more likely to have their HTN recognized within 6 months as compared to patients seen at usual care clinics, and that recognition of HTN will be more likely for patients seen at high-intensity rather than low-intensity clinics. Generalized linear mixed-model regression with a logit link and binomial error distribution may be used to test the effect of the interventions following the same analytic strategy and equations for H1 and H3 above, with the substitution of HTN recognition as an endpoint in place of BP re-measurement, and the use of patient-level covariates of the lowest SBP percentile at the index visit, and BMI percentile at the index visit. Study arm contrasts will test differences in BP recognition for CDS (low-intensity or high-intensity) vs. Usual care and high-intensity vs. low-intensity. Statistically significant study arm contrasts (alpha=.05) and parameters in the expected direction will support the H3 and H4 predictions stated for Aim 2.

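### The H3/H4 model adjusts for the lowest SBP percentile at the index visit, a value the CDS repeat prompt can change; the size and direction of the resulting shift cannot be settled from the documents

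*Combined protocol and SAP*

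**What the plan says.** - **H3/H4 model (section 8.4).** A logit mixed model "may be used to test the effect of the interventions", with "the use of patient-level covariates of the lowest SBP percentile at the index visit, and BMI percentile at the index visit". Section 8.4.1 has the management endpoints follow the H3 approach.
- **H1/H2 model (section 8.4).** The clinic randomisation factors "and patient-level covariates of age, sex, and SBP percentile of the elevated BP". That SBP is the value that triggers the prompt.
- **The intervention (section 6.1.1).** The second CDS component prompts a repeat once an elevated BP has been entered. The third classifies the child on the lowest SBP of the visit, or on what is available if nothing was repeated.
- **Expected effect on repeats (section 8.1).** H1: "Youth with elevated BP measured at a PedsBP intervention clinic will be more likely to have a repeat BP" measurement than in usual care. H2: "Youth with elevated BP measured at a high-intensity PedsBP clinic will be more likely to have a repeat BP measurement during their visit" than at a low-intensity clinic.
- **Analysis sets (section 8.1, Table 2).** The H1/H2 denominator begins "First BP at visit". The H3/H4 denominator is "BP at visit and at least 2 of 4 prior BPs, within last 2 years", without saying whether the first or the lowest reading of the visit counts.

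**The concern.** The lowest SBP of the visit equals the first reading unless a repeat is taken and is lower. Prompting repeats is part of what is randomised. If Aim 1 succeeds, the Aim 2 covariate is lower in CDS than in usual care among children with the same first reading, and likewise in high- than in low-intensity clinics. Adjusting for it then compares children with equal final readings but, on average, different first readings.

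HTN recognition is one of the two primary outcomes, and the secondary models inherit the choice. Table 2 adds a second route. If the lowest reading defines the H3/H4 set, a prompted repeat that comes down can take a child out of the set, so entry also depends on arm.

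**Working it through.** **1. The plan's own figure.** Inputs from section 8.4: 24 patients per clinic, ICC 0.035, 15 usual care and 30 CDS clinics, 20% versus 37%.
- Design effect = 1 + (24 − 1) × 0.035 = 1.805. Effective n = 360/1.805 = 199.4 and 720/1.805 = 398.9.
- SE of the difference = √(0.20×0.80/199.4 + 0.37×0.63/398.9) = 0.0372. Power = Φ(0.17/0.0372 − 1.96) = Φ(2.6), above 99%. The stated 99% reproduces, and the covariate choice does not alter it.
- Design odds ratio (OR) = (0.37/0.63)/(0.20/0.80) = 2.35. Minimum detectable OR: H3 (0.31/0.69)/(0.20/0.80) = 1.80; H4 (0.44/0.56)/(0.30/0.70) = 1.83.

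**2. What the documents do not give.** The repeat rates in section 8.4 (28%/47% in the earlier trial, 30%/45% and 40%/50% in planning) belong to Aim 1: "Aim 1 outcomes will be assessed in the context of care provided at the index visit with an isolated hypertensive BP recorded". Using them for the H3/H4 set is an assumption. So are all SBP variances and slopes below.

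**3. Mechanism by hand.** Gap between arms in mean lowest SBP = (difference in repeat rates) × (mean fall from first to lowest reading when repeated). In the simulation below, with the first reading defining the set and 30%/45% repeats, the gap is 0.5–1.3 mmHg. The implied mean fall is 0.5/0.15 = 3.3 to 1.3/0.15 = 8.7 mmHg. If recognition follows the lowest reading with log-odds slope 0.04–0.08 per mmHg, the pathway through the repeat is worth exp(−0.04×0.5) = 0.98 to exp(−0.08×1.3) = 0.90 on the OR scale. Adjusting for the lowest reading removes that pathway; adjusting for the first keeps it.

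**4. Simulation with no direct CDS effect.** Assumed: usual SBP mean 112, SD 11; visit SD 6; within-visit SD 5 or 7; second reading 0, 2 or 4 mmHg lower; threshold 130; at least 2 of 4 prior visits elevated; repeats at random among elevated first readings; 20% recognition at the mean; slope 0.04 or 0.08 per mmHg. A variant adds diastolic BP. Repeat rates are 30%/45%; ORs are on the percentile scale.

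| Set defined by | Recognition follows | OR, lowest-reading covariate | OR, first-reading covariate |
|---|---|---|---|
| First reading | usual or first BP | 1.01–1.05 | 1.00 |
| First reading | lowest reading | 0.98–1.00 | 0.91–0.98 |
| Lowest reading | usual or first BP | 1.01–1.04 | 1.00–1.02 |
| Lowest reading | lowest reading | 0.99–1.00 | 0.96–0.99 |

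With recognition following usual or first BP, the planned model gives at most 1.06 at 28%/47% and, for H4 at 40%/50%, at most 1.03.

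**5. Size against sampling error.** With 353 versus 707 patients, effective n is 196 and 392. At 20% in both arms, SE(log OR) = √(1/(196×0.16) + 1/(392×0.16)) = 0.219. ln 1.05 = 0.049, and 0.049/0.219 = 0.22 SE. Two-sided type I error = 1 − Φ(1.96 − 0.22) + Φ(−1.96 − 0.22), about 5.6%.

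**6. Does the direction hold when assumptions change?**
- Zero slope, or equal repeat rates: no shift.
- True OR 2.35, first-reading set, recognition following the first reading: 2.275 with the lowest-reading covariate, 2.296 with the first. The shift goes against CDS.
- Usual care repeating mainly the highest readings, lowest-reading set: 1.085 against 1.092. Again against CDS.
- Recognition falling with SBP: the log OR moves by about −0.06 (28%/47%, separate assumptions).

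Over those wider assumptions, at the documents' repeat rates, the difference in log OR between the two models ran from about −0.09 to +0.16.

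**7. Entry to the set.** In usual care the lowest-reading set is 14–27% smaller than the first-reading set. Within the lowest-reading set, the CDS denominator is a further 4–9% smaller at 30%/45%.

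**The case against.** Much of the case for the plan stands.

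- **Aim 1 is not a true precedent.** There the repeat is the outcome, so the lowest reading could not sensibly be a covariate. The contrast shows that a pre-prompt value is already in use, not that the plan contradicts itself.
- **The lowest reading matches how the CDS classifies the child.** If clinicians act on it, recognition given the final visit BP is a legitimate target. The first-reading model then answers a different question: the total effect, including what the repeat does.
- **The swap is not neutral.** If recognition follows the lowest reading, a null OR near 1.00 becomes 0.91–0.99. This is why both models should be reported.
- **The shift is small.** An OR of 1.05 could not produce 2.35, or even the minimum detectable 1.80.

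A reader might go further and infer that the planned covariate always favours CDS. The documents do not support that. They do not say how recognition depends on SBP or which elevated readings usual care repeats, and step 6 shows reversals under plausible alternatives. Nor does the phrase fit H4, where both arms have the CDS and the contrast is high against low intensity.

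What the objection leaves untouched is that a primary-outcome model conditions on a value the intervention is expected to change. With the sign unknown, the planned estimate cannot be defended as conservative either.

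**Conclusion.** The concern holds in a limited form. The H3/H4 covariate can be affected by the intervention through the repeat prompt, nothing elsewhere in the documents corrects this, and the management models inherit it. Size and direction are unknown from the documents. Under the step 4 assumptions, the shift usually favours the arm with more repeats; where recognition follows usual or first BP, the null OR is at most about 1.05 at 30%/45% on the percentile scale, roughly a fifth of a standard error. It can be nil or reverse under other mechanisms. Part of the issue is a choice of estimand that the plan has not stated.

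The undefined reading in Table 2 is part of the same problem, because it decides whether entry to the set also depends on arm.

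These results take the index visit to be the one at which HTN criteria are met, borrow Aim 1 repeat rates, and use assumed SBP variances and slopes. The age 6–12 percentile thresholds were not simulated, and clustering enters only through the design effect. The change is worth making because the outcome is primary and the remedy is nearly free, not because the expected distortion is large.

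**What to change.** 1. In section 8.4, for H3/H4 and the secondary models that follow H3, replace the lowest-reading covariate with the SBP percentile of the first reading at the index visit. Keep the lowest-reading model as a sensitivity analysis and say which effect each model estimates.
2. In Table 2, state whether the first or the lowest reading defines the visit BP for the H3/H4 set. If it is the lowest, add a sensitivity analysis in the set defined by the first reading, applied identically in all arms, and report by arm the number meeting HTN criteria per eligible patient.

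**Cost.** One phrase, one clause and one or two extra models. H1/H2 already require the first reading, and sample size and power do not change.

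**Downsides.** If the set is defined by the lowest reading, the first reading is itself slightly unbalanced (residual null OR up to 1.02). A first-reading set includes children whose repeat is normal (simulated 7–14% in usual care, 11–21% in CDS at 30%/45%), which may dilute the effect. The staff education on BP measurement in section 7.1 could also move first readings a little.

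This concerns the analysis only, not how the CDS classifies patients in care.

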1.1 SYNOPSIS

Title:	Improving Recognition and Management of Hypertension in Youth: Comparing Approaches for Extending Effective CDS for use in a Large Rural Health System
Grant Number:	AHRQ 1R18HS027402-01A1
Study Description:	This research project will adapt the PedsBP clinical decision support (CDS) tool for use at Essentia Health and measure the implementation processes and outcomes. This minimal risk, pragmatic trial will randomize up to 45 Essentia clinics in a 3-arm, cluster-randomized trial. Clinics will be randomly allocated in a 1:1:1 allocation ratio to usual care, low-intensity implementation, or high-intensity implementation of the PedsBP CDS. Study-eligible patients will be allocated to the study arm assigned to the clinic at which the patient has an index visit when blood pressure (BP) is measured. Clinic providers and rooming staff will be interviewed and surveyed to assess experience and satisfaction with the CDS.
Objectives:	Identify optimal intervention implementation strategies for the PedsBP CDS tool. Post-implementation comparisons of high- plus low-intensity implementation versus usual care and high- versus low-intensity implementation will be conducted for the primary endpoints of BP remeasurement at the index visit (for patients with an elevated first BP), and BP recognition within 6 months of the index visit (for patients newly meeting HTN criteria).
Endpoints:	There are two primary outcomes. One is repeat BP measurement during the same clinic visit, of an initial BP that is \geq 95th percentile for children 6-12 years or \geq 130/80 mmHg for adolescents 13-17 years. Repeat BPs can be measured by providers or rooming staff but will only contribute to this outcome if recorded in the vitals section of the EHR. The other primary outcome is clinical recognition of HTN within 6 months of meeting criteria for HTN. Clinical recognition will include a new diagnosis of HTN (ICD-10: I10) or elevated BP (ICD-10: R03), adding HTN or elevated BP to the problem list. Secondary outcomes will describe management within 6 months of meeting criteria for HTN including: lifestyle counseling, dietitian referrals, subspecialty referrals, initiation of antihypertensive medications and receipt of diagnostic imaging (echocardiogram or renal ultrasound). BP control at 12 months following the index date meeting criteria for HTN will be an exploratory outcome.

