5.1 INCLUSION CRITERIA

Patients will be eligible for the PedsBP CDS tool if:

- a) 6-17 years of age
- b) BP measured and entered in the vital sign section during an ambulatory primary care visit in a randomized primary care clinic
- c) not pregnant or postpartum

Patients must meet these eligibility criteria to be included into study analyses:

- a) have at least one index visit to a randomized primary care clinic in the intervention period
- b) meet eligibility for PedsBP CDS at index visit
- c) no previous HTN diagnosis prior to index visit
- d) not taking antihypertensive medication prior to index visit
- e) not opted out of use of their data for research via general consent prior to performing analyses

Primary care providers must meet these eligibility criteria to participate in this study:

- a) practice at a randomized primary care clinic
- b) be a pediatric or family medicine care provider (pediatrician, family physician, nurse practitioner or physician assistant), and
- c) provide ongoing clinical care for children and adolescents

Provider and rooming staff inclusion criteria for interviews and surveys are provided in separate protocols.

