5.2 EXCLUSION CRITERIA

Patients will be excluded from analyses if the following criteria are met:

- a) outside of the inclusion age range (<6 years and ≥ 18 years) at index visit
- b) pregnant or postpartum adolescents during study period
- c) known HTN diagnosis or taking antihypertensive medication at index visit
- d) opted out of use of their data for research via general consent prior to performing analyses

Provider and rooming staff exclusion criteria for interviews and surveys are provided in separate protocols.

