6.2 RANDOMIZATION STRATEGY

Covariate-based constrained randomization⁹⁸ may be used to enhance study arm balance on key factors during randomization of the clinics in this cluster-randomized trial. This method permits the use of multiple balance factors and can yield improved study arm balance and increased statistical power beyond simple randomization when balance factors are included in both the design and analysis phase⁹⁹ of the study. Clinic-level attributes of clinics and patient mix to be used as balance factors will be obtained via EHR data and ascertained for care in clinics in the 18 months prior to randomization. Proposed clinic-level balance factors include baseline levels of BP re-measurement and HTN recognition, number of visits with patients age 6-17 (ranging from 145 to 6556 patients per clinic over 18 months in preparatory data), location (metropolitan/micropolitan (20 clinics) versus small town/rural (25 clinics)), and proportion of public pay patients (ranging from 13% to 73%). Randomization will be carried out with the CCR macro for use within SAS¹⁰⁰, and conducted one month prior to implementation of the low- and high-intensity strategies in clinics.

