Data required for PedsBP CDS-enhanced care will be sent to HPI for PedsBP operations. CDS data is retained in the transactional data store with minimal access until needed for analysis. With respect to the transactional data store, the following measures will be taken to protect PCPs and patients from the risk of breach of confidentiality: A unique study ID code unrelated to the medical record number or other study subject-specific information will be assigned to each patient at the index visit (first visit in the intervention period). The study ID is used to link data from patient encounters over time and various data sources that are needed for analysis. All index and subsequent encounter data for eligible patients, including vitals, medications and diagnoses, are securely stored behind a firewall within a limited de-identified dataset.

A crosswalk table linking this code number to a medical record number or patient name will be created by EH programmers in order to 1) check against opt out lists, and 2) link to study outcomes. EIRH Informatics Analysts assigned to this research project will exclude patients who have opted out via general consent; data for these patients will not be stored in analytic data files. The data for patients who have opted out of external research will be deleted from analyses files. The crosswalk will be destroyed within 12 months after completion of the linked databases needed to test study hypotheses. This project will be governed by a Business Associates Agreement, DUA, and appropriate services agreements.

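### The H3/H4 model ignores each child's pre-trial elevated-BP (R03) status, a likely strong predictor of recognition, and the plan does not say whether a repeat R03 counts as new

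*Combined protocol and SAP*

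**What the plan says.** - **Outcome.** The Synopsis (Section 1.1, Endpoints) counts as recognition "a new diagnosis of HTN (ICD-10: I10) or elevated BP (ICD-10: R03), adding HTN or elevated BP to the problem list". It does not say how *new* applies to a child who already carries R03.
- **Eligibility.** Section 5.1 requires "no previous HTN diagnosis prior to index visit", and Section 5.2 removes children with "known HTN diagnosis or taking antihypertensive medication at index visit". Neither mentions an earlier elevated-BP code.
- **Denominator.** Table 2 (Section 8.1) defines the H3/H4 population by "BP at visit and at least 2 of 4 prior BPs, within last 2 years", all in the hypertensive range.
- **Model.** Section 8.4 specifies for Aim 2 "the use of patient-level covariates of the lowest SBP percentile at the index visit, and BMI percentile at the index visit". There is no patient-level term for an earlier R03.
- **Clinic level.** Section 6.2 states: "Proposed clinic-level balance factors include baseline levels of BP re-measurement and HTN recognition". Section 8.4 carries the factors used in randomization into the model. These are clinic averages.

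**The concern.** Freedom from the outcome at baseline is enforced for one scoring code (I10) but not for the other (R03). The denominator makes an earlier R03 plausible. Section 2.2 defines HTN by elevation at three separate visits, so a clinician who noticed the first or second high reading would more naturally have coded elevated BP than HTN.

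Scoring for such a child depends on a rule that the plan does not give. If *new* is literal, another R03 cannot score, and only a first HTN diagnosis or a fresh problem-list entry can. If a repeat R03 counts, the child may score easily in any arm. Either way, prior R03 status should predict the outcome strongly, and the model cannot see it. At stake are the precision of a primary contrast and the meaning of the recognition rate, which would mix new with earlier recognition if repeat codes count.

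**Working it through.** **Inputs (Sections 8.2 and 8.4).** 1060 patients in 45 clinics; ICC 0.035; two-sided alpha 0.05. H3 compares 15 with 30 clinics at 20% vs 37% (99% power) and 20% vs 31% (80% power). H4 compares 15 with 15 clinics at 30% vs 44% (80% power).

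**Method.** Cluster size m = 1060/45 = 23.56. Design effect = 1 + (23.56 − 1) × 0.035 = 1.789. Effective sizes are 15 × 23.56/1.789 = 197.5 and 30 × 23.56/1.789 = 394.9. Power = Φ[(d − 1.96 × SE0)/SE1], where SE0 uses the pooled rate and SE1 the separate rates.

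**The plan's figures first.**
- H3, 20% vs 37%: (0.17 − 1.96 × 0.0404)/0.0374 gives 0.992 (stated 99%).
- H3, 20% vs 31%: (0.11 − 1.96 × 0.0388)/0.0368 gives 0.82. The detectable difference at 80% power is 10.7 points (stated 11).
- H4, 30% vs 44%: (0.14 − 1.96 × 0.0486)/0.0481 gives 0.82. The detectable difference is 13.6 points (stated 14).

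The stated figures reproduce to rounding. With unpooled variance the last two powers are 0.849 and 0.829.

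**Children with pre-trial R03.** Their share f is not in the documents; I assume 5%, 10% and 20%. For the two extremes, suppose they show no arm difference and all score 0 or all score 1. The rate in each arm becomes (1 − f)p or f + (1 − f)p, and the difference shrinks by the factor (1 − f). At f = 10%, 11 points become 9.9. If they are excluded instead, the other rates are unchanged and cluster size is m(1 − f).

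| Case | f | Kept, score 0 | Kept, score 1 | Excluded |
|---|---|---|---|---|
| H3 20% vs 31% | 5% | 0.794 | 0.745 | 0.810 |
| | 10% | 0.763 | 0.670 | 0.798 |
| | 20% | 0.696 | 0.535 | 0.770 |
| H3 20% vs 37% | 10% | 0.982 | 0.958 | 0.989 |
| | 20% | 0.963 | 0.885 | 0.984 |
| H4 30% vs 44% | 10% | 0.759 | 0.716 | 0.802 |
| | 20% | 0.685 | 0.605 | 0.774 |

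For H3 at 20% vs 31%, keeping these children rather than excluding them costs 1.6 points (0.810 − 0.794) to 7.4 points (0.770 − 0.696) if they never score. It costs 6.5 points (0.810 − 0.745) to 23.5 points (0.770 − 0.535) if they always score.

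**How plausible is the upper extreme?** If 20% always score and the rest are recognised at 20%, overall usual-care recognition is 0.20 + 0.80 × 0.20 = 36%. The plan assumes 20% and cites 21% from the earlier trial. Large shares combined with certain scoring therefore fit the plan's own rate poorly.

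**If these children respond like the others.** Nothing is diluted. Keeping everyone gives 0.82, and excluding 20% gives 0.77.

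**Covariate instead of exclusion.** In simulations of the planned logit analysis, a pre-go-live R03 indicator essentially matched or improved unadjusted power in every scenario tried. With a 20% share recognised at 90% in both arms, power rose from 0.64 to 0.74. Where these children did respond (20% share), keeping them gave about 0.88 and excluding them about 0.78.

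**The case against.** A reader might infer that these children enter with the outcome already present, that the arm contrast is therefore biased or certainly diluted, and that they should leave the primary population. The documents do not support this.

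- The Synopsis requires a new diagnosis or an addition to the problem list, so an old R03 is not itself an event.
- Codes entered before go-live cannot be a consequence of arm. The issue is precision and interpretation, not bias between arms.
- Dilution requires that these children show little arm difference. A first I10 in a child previously coded R03 still scores. The CDS is built to flag that such a child now meets HTN criteria (Section 6.1.1), so this step may be a real CDS effect. Exclusion would discard it and narrow the population that the Synopsis names.
- The share is assumed. The 26% in Section 2.2 is a background figure for any HTN or elevated-BP diagnosis, not a prior-R03 rate at these clinics. For children who qualify late in the 18 months, the earlier readings may fall after go-live.

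All of this stands. Two further replies carry less weight. Baseline recognition may enter through the clinic-level factors, but Section 6.2 only proposes them, and a clinic average cannot show which child was already coded. Definitions are to be adapted from the earlier trial (Section 9.1.5.1) and variables listed in a separate data dictionary (Appendix 1). Either may settle the matter, but the rule for a primary outcome should be visible in the plan.

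**Conclusion.** The gap is real but moderate. R03 scores toward H3/H4, a pre-trial R03 is neither excluded nor modelled at patient level, and *new* has no rule for a child already coded. The cost is lost precision and, if repeat codes count, a recognition rate that mixes new with earlier recognition.

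The size depends on two unknowns: the share of such children and how they score. The tabulated losses also assume no arm difference among them; with the same response as other children there is no loss. The smaller H3 effect and H4 are the exposed cases. The 20% vs 37% case stays well powered at a 10% share. Nothing here shows that the stated power is wrong or that primary exclusion is needed.

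**What to change.** 1. **Section 8.4.** Add to the H3/H4 patient-level covariates a yes/no indicator of any R03 encounter code, or active elevated-BP problem-list entry, recorded before go-live (August 2022). Use only pre-go-live entries. An R03 entered later, but before the child meets HTN criteria, may itself be a CDS effect. Anchor the cut-off to go-live rather than to the index visit, a term the plan uses both for a child's first visit in the intervention period (Section 8.3) and for the qualifying visit.
2. **Section 1.1, Endpoints.** State whether a repeat R03 counts as new for these children, with the same rule in all arms.
3. **Analysis set.** Keep every child newly meeting HTN criteria in the primary analysis. Report the analysis without children who had pre-go-live R03 as a sensitivity analysis.

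The cost is one covariate, one sentence and one extra model run, plus a patient-level extract of earlier R03 entries. Section 6.2 describes only clinic-level baseline data, so that extract may be new work, although Appendix 1 already plans to draw EHR history from before the index visit. The indicator does not restore a risk difference shrunk by children who cannot respond; it recovers precision. The adjusted odds ratio is conditional on prior R03 and should be reported as such.
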